Damage progression will be evaluated by the change in total Sharp/van der Heijde damage score of hands and forefeet. It is known that this variable has a positively skewed distribution. Cumulative probability plot with the distribution of change in total Sharp/van der Heijde score from baseline to two-year follow-up will be applied as well as a non-parametric test (the Mann-Whitney test) to compare intervention and control groups.

Harm

The primary outcome variable for harm is operationalized as a binary variable with two categories (0= no adverse event, 1= at least one adverse event of special interest (see 9.1.1.a). This variable will be presented as a proportion. A chi-square test will be used to test for differences between the proportion of adverse events in intervention and control groups.

Secondary analyses:

A logistic regression model with harm as dependent variable will be fitted in order to adjust for potential factors that may alter the probability of AEs (as explained above for benefit). In addition absolute incremental risk and relative risk will be calculated for all major events, with confidence intervals.

Analysis strategy:

- One-sided significance levels (alpha=0.05); asymmetric null hypotheses: this approach increases the chance of rejecting the null hypotheses compared to standard two-sided testing. This results in a higher chance of declaring benefit (justified in view of scientific knowledge and the pragmatic trial design), but also a higher chance of declaring harm (to guard against the limited power of the study to detect harm).
 - confirmation of benefit: on the basis of the trial data we expect to reject the null hypothesis of GC (added to standard of care) yielding similar effectiveness compared to placebo (H_0); the alternative (H_1) hypothesis is that GC yields better effectiveness;
 - demonstration of absence of harm: we expect NOT to reject the null hypothesis that GC yields similar side effects; see 4.4 for considerations of the 95% non-inferiority confidence bound.
 - In case the trial detects a difference in AEs favoring the GC group, the superiority of GC will be tested in a secondary analysis.

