11.2 Secondary study outcome(s)

For continuous variables, (e.g. RA core, SF36, RAID, QALY) first univariate analyses will be conducted to evaluate their distributions and the presence of outliers. If the variables are not normally distributed they will be transformed. Then mixed regression models will be used to study changes in their levels over the follow-up.

For categorical variables (e.g. ACR response, EULAR response) multiple exclusive groups will be defined and differences between the intervention and control groups will be tested by a chi-squared test for linear-by-linear association. In secondary analyses, generalized linear mixed models (GLMM) will be used to assess different

patterns of change during the follow-up. Finally, number needed to treat and number needed to harm analyses will be conducted on selected categorical variables based on the observed events in the placebo group.

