#### 4.13 Analysis of secondary outcome variables

We will estimate and test for the detrimental effects of prednisolone on bone mass and incident fracture rate.

1. Continuous outcomes: bone mass lumbar spine, bone mass hip: analyzed according to model 1
2. Discrete outcome: presence of at least one incident compression fracture (by VFA or lateral spine films): analyzed according to model 2

Tests will be one-sided at  $p < 0.05$ , with Benjamini-Hochberg adjustment for multiple testing.

We will report the results of the other secondary outcome variables descriptively with means/proportions and 95%CI per treatment group per time point.

3. Variables measured at every clinic visit
  - a. Continuous outcomes: patient and physician global assessment of disease activity, joint counts (swollen joints and tender joints), acute phase reactants (C-reactive protein (CRP) and erythrocyte sedimentation rate (ESR)); vital signs, lab (blood) variables; adherence by pill count and by electronic adherence cap.
  - b. Discrete outcomes: patients with at least one instance of remission; of minimal disease activity; patients with at least one long-term period (2 consecutive instances 6 months apart) of remission; of minimal disease activity
4. Variables measured at every visit (clinic and remote):
  - a. Continuous outcomes: severity and duration of morning stiffness, RA Impact of disease (total score, and components pain and fatigue analyzed separately), RAPID3 index, EuroQoL, m(HAQ)
  - b. Discrete outcomes: discontinuations of study drug, of with reason; all changes of antirheumatic treatment, with reason; joint replacement surgery
  - c. Expressed as survival curve: discontinuation of study drug over time
5. Variables measured at baseline and end of study:
  - a. Continuous outcomes: DAS44, SF36 (domains and summary mental and physical component scores), 57-symptom list;
  - b. Discrete outcome: number of incident compression fractures (by VFA or lateral spine films)
6. Variables measured only at baseline:
  - a. Continuous/discrete: Demographics, education and medical history; Morisky medication adherence scale (MMAS-8), health literacy, arthritis helplessness index questionnaires; number of prevalent vertebral fractures (by VFA or lateral spine films), distribution of % height loss in vertebrae with fractures.
7. Response indices calculated at 3 months in the PP analysis (discrete): ACR20, 50, 70; EULAR response.

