Listing 11	Change of antirheumatic treatment, with reason
Listing 12	Intensification of treatment for existing comorbidity, e.g. hypertension or diabetes
Listing 13	DAS28 scores, DAS44 scores and EULAR response
Listing 14	Swollen and tender joints
Listing 15.A	Patient global assessment of disease
Listing 15.B	Physician global assessment of disease
Listing 16	ACR 20 response
Listing 17	Minimal disease activity
Listing 18	Total Sharp/van der Heijde damage score of hands and forefeet radiographs
Listing 19	Morning stiffness
Listing 20.A	SF-36 questionnaire
Listing 20.B	SF-36 scores
Listing 21.A	(m)HAQ questionnaire
Listing 21.B	(m)HAQ scores
Listing 22.A	RAID questionnaire
Listing 22.B	RAID scores
Listing 23.A	EQ-5D questionnaire
Listing 23.B	EQ-5D scores
Listing 24	Patient symptom list questionnaire
Listing 25.A	Laboratory – Hematology and chemistry
Listing 25.B	Laboratory – Lipids
Listing 25.C	Laboratory – CRP and ESR
Listing 26	Vital signs
Listing 27	Physical examination
Listing 28	Previous medication
Listing 29	Concomitant medications
Listing 30.A	Adverse events
Listing 30.B	Serious adverse events
Listing 30.C	Other adverse events of special interest
Listing 31	Death

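### Most secondary outcomes, including most secondary harms and the individual AESI types, have no planned between-arm estimate, although the protocol planned comparisons

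*SAP*

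**What the plan says.** SAP 4.13 picks out three outcomes for estimation and testing. For the first two it says "bone mass lumbar spine, bone mass hip: analyzed according to model 1", and for the third "presence of at least one incident compression fracture (by VFA or lateral spine films): analyzed according to model 2". These tests are one-sided at 0.05, "with Benjamini-Hochberg adjustment for multiple testing". For the rest: "We will report the results of the other secondary outcome variables descriptively with means/proportions and 95%CI per treatment group per time point". Drug discontinuation is also shown as a survival curve.

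The shells in SAP section 7 are per-arm summaries: a mean with SD (some with a 95% CI), or a number and percentage. The one shell for model output is Table 9, the primary DAS28 analysis. Tables 36A to 36D give counts or means of AEs, SAEs and other AESIs, overall or by organ system, without a CI or a contrast. SAP 1.4.2 lists intensified treatment of existing comorbidity as a secondary harm endpoint. It is not in 4.13 or the tables; it appears only as Listing 12, "Intensification of treatment for existing comorbidity, e.g. hypertension or diabetes".

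The protocol planned more. For harm, 11.1 says: "In addition absolute incremental risk and relative risk will be calculated for all major events, with confidence intervals". For continuous secondary outcomes, 11.2 first checks distributions and transforms where needed: "Then mixed regression models will be used to study changes in their levels over the follow-up". For categorical outcomes, "differences between the intervention and control groups will be tested by a chi-squared test for linear-by-linear association", with generalized linear mixed models and numbers needed to treat or harm to follow.

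SAP section 1 undertakes to document differences from the protocol. The part of Appendix B on secondary endpoints deals only with fatigue and with retention on study drug.

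**The concern.** The trial asks about the balance of benefit and harm of low-dose prednisolone in older patients. Much of that balance lies in the secondary outcomes: pain, function, quality of life, blood pressure, glucose, infection and new diabetes. For these the plan describes each arm separately and stops. The quantity that randomisation supports, the difference between arms with its uncertainty, is not prespecified.

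Two things are at stake. A reader given two intervals may compare them by eye, which is a much stricter criterion than an interval for the difference. And any contrast calculated later will be post hoc, with the choice of model, covariates and scale made after the results are known. For harms the gap is sharper, because the composite can hide opposite movements in its components and no component gets its own effect estimate.

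**Working it through.** **1. Protocol and SAP side by side**

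| Outcome group | Protocol | SAP 4.13 and section 7 |
|---|---|---|
| Continuous secondary (core set, SF-36, RAID) | 11.2: mixed models | Per-arm means |
| Categorical secondary (ACR, EULAR response) | 11.2: between-group test, mixed models, NNT/NNH | Per-arm percentages |
| Major adverse events | 11.1: absolute and relative risk with CI | Tables 36A-D: no CI, no contrast; AESI types not shown singly |
| Intensified treatment of comorbidity | Secondary harm (9.1.1) | Listing 12 only |

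Between-arm analyses that do remain in the SAP:
- bone mass and incident fracture (4.13);
- 3-month DAS28 in the per-protocol population (4.8.2 and 4.10.1.1);
- Z-tests on first lasting co-medication changes between months 3 and 15 (4.11.1), used as a confounding check;
- the primary harm composite, as a relative risk (4.10.3).

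Costs and QALYs go to a separate plan.

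**2. The plan's own power figure**

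Neither document gives power for secondary outcomes. The nearest figure is for primary harm (protocol 6.4, SAP section 6): 34% versus 46%, 400 patients, one-sided 5%, 80% power. With the pooled-variance formula and n = 200 per arm:

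Power = Φ[(0.12·√200 − 1.645·√(2·0.40·0.60)) / √(0.34·0.66 + 0.46·0.54)] = Φ[(1.697 − 1.140)/0.688] = Φ(0.81) = 79.1%.

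This agrees with the stated 80%.

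**3. The same rates reported two ways, 225 per arm (Wald intervals)**

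- Per arm: SEs are √(0.34·0.66/225) = 0.0316 and √(0.46·0.54/225) = 0.0332. The 95% CIs are 27.8% to 40.2% and 39.5% to 52.5%. They overlap.
- As a contrast: SE = √(0.0316² + 0.0332²) = 0.0458. The difference is 12.0 points (95% CI 3.0 to 21.0), two-sided p = 0.009 by the pooled test. The relative risk is 1.35 (1.07 to 1.70).

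The rates are borrowed from the primary harm composite for illustration; that composite does get a direct comparison.

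**4. General size of the loss**

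With equal standard errors s, two 95% intervals separate when the difference exceeds 2·1.96·s, while the difference itself has standard error √2·s. Separation therefore needs z = 1.96·√2 = 2.77, two-sided p = 0.006. A difference with 80% power in a two-sided 5% test has expected z = 1.96 + 0.84 = 2.80. The intervals separate with probability Φ(2.80 − 2.77), about 51%.

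**5. Continuous outcomes: effect of the baseline**

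Neither document gives the correlation ρ between baseline and follow-up; I assume 0.5 to 0.7. Start from 80% power for a baseline-adjusted difference (z = 2.80) and assume equal variances at both times.

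- Raw follow-up values: expected z = 2.80·√(1 − ρ²), i.e. 2.42 to 2.00.
- Change from baseline: expected z = 2.80·√((1 + ρ)/2), i.e. 2.42 to 2.58.

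| Shown per arm as | Power of direct unadjusted test | Probability that the two CIs separate |
|---|---|---|
| Raw follow-up value, ρ 0.5 to 0.7 | 68% to 52% | 36% to 22% |
| Change from baseline, ρ 0.5 to 0.7 | 68% to 73% | 36% to 42% |

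The first row fits RAID, HAQ, stiffness and joint counts, and CRP in Table 15. The second fits laboratory values (Table 28 also shows CRP this way), vital signs, and the 0-24 month changes in SF-36, DAS44 and symptom count. Neither row applies to binary outcomes.

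**The case against.** A descriptive approach to a long list of secondary outcomes is a defensible way to limit false positives, and the SAP does compare arms on several items outside 4.13. That much stands. But multiplicity argues against unplanned p-values, not against estimates.

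It can also be said that a reader may subtract one arm from the other. Where mean, SD and n are given, a crude difference and interval can indeed be derived. It would lack the adjustment for baseline, strata and centre used in models 1 and 2, and it fails where the shells switch to median, minimum and maximum.

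On the protocol's promise, the sentence on continuous outcomes names mixed models without naming a group contrast, and major events are not defined. The explicit between-group commitments are for categorical outcomes and major events, and for adherence in 11.1.

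Three stronger readings are tempting, and the documents do not support them:
- **Baseline is ignored throughout.** It is not: many shells report change from baseline.
- **The plan judges effects by overlap of intervals.** No section sets such a rule. Several shells (AEs, laboratory values, vital signs, most SF-36 rows) do not even show the CI that 4.13 announces.
- **EQ-5D is never compared.** Protocol 11.1 uses the difference in QALYs in the economic evaluation, whose plan is separate and not available here. Only a per-visit EQ-5D contrast is absent from this SAP.

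**Conclusion.** The point holds for most secondary outcomes. The SAP replaces planned comparisons with per-arm description, and the available Appendix B text does not say so; text missing from the copy reviewed could alter that last statement. The primary conclusions are unaffected, but the secondary part of the benefit and harm question is left without prespecified effect estimates. This should be changed before unblinding.

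A reader might infer that all but three secondary outcomes go without a comparison, or that the randomised contrast is never estimated. That is too strong. The count of three is right for 4.13 alone; 3-month DAS28 is also modelled, and a restricted form of treatment change is tested. The three outcomes in 4.13 are themselves harms, and the primary harm composite gets a relative risk.

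On size, the 51% figure assumes equal standard errors. The ranges for continuous outcomes also rest on the assumed correlation of 0.5 to 0.7. They measure what is lost if readers compare intervals by eye, which the plan does not instruct them to do.

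**What to change.** In SAP 4.13, after the per-arm summaries, add: and as a between-group difference with 95% CI. Label these as estimates, without p-values. Then specify:

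- **Repeated continuous outcomes:** a model of the form of model 1, with the outcome's own baseline and its own visits. Model 1 codes five post-baseline occasions; RAID and stiffness have eight up to month 24. HAQ alternates between full and modified versions, so say how these are combined. Transform or bootstrap if strongly skewed.
- **Outcomes at 0 and 24 months:** the form of model 2.
- **Binary outcomes, each AESI type, and intensified treatment among patients who had the condition at baseline:** risk difference and relative risk with 95% CI.

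Add matching columns to the section 7 shells, and tables for AESI types and intensification. Record any remaining departure from protocol 11.1 and 11.2 in Appendix B, with the reason.

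While editing 4.13, check its model references: model 1 is for repeated measures but bone mass has one follow-up value, and model 2 is linear but fracture is binary.

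The cost is some extra model code, since models 1 and 2 need adapting and binary outcomes need their own, plus longer tables. No new data are needed.

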## 5 Interim analyses

No interim analyses were planned. However, we performed a new sample size calculation based on blinded AE incidence rates halfway through the trial (see below).

## 6 Sample size and power calculations

In the main GLORIA trial, 225 patients per treatment group will be entered (total 450 patients).

In the chosen analysis strategy (see section 4), to detect differences in benefit (disease activity, radiographs) extensive RA trial experience (both for GC and other agents) has shown a sample size of 200 patients per group is amply sufficient. For example, in the CAPRA-2 study that compared modified release prednisone 5mg/d against placebo, the prednisone group had 231 patients, the placebo group 119 patients. The change in DAS28 after 3 months of treatment was  $-1.15$  in the prednisone group,  $-0.63$  in the placebo group; difference  $-0.52$  (SE 0.13,  $p<0.001$ ) (Buttgereit, 2013). However, the true incidence of adverse events (AEs) for GCs is currently unknown. Most relevant data to assess sample size adequacy for this study come from the reported CAMERA-2 trial (Bakker, 2012). This trial randomized 236 early RA patients to tight-control high-dose methotrexate plus 10 mg prednisolone or placebo for two years. Interestingly, 22% of placebo patients compared to only 14% of prednisolone patients reported at least one serious AE or clinical event as defined in our protocol.

The original protocol used a base case expectation for a total of 20% of patients experiencing at least one event over two years in the placebo group and calculated a need for 400 patients in each treatment group, to have about 80% power to detect an increase of 7% (from 20% to 27% events; 90% power for an increase of 9%). However, based on our current experience the sample can be decreased to about 450 instead of 800.

Elaboration:

In December 2018 we had >400 patients in the trial with a mean follow up of 9 months, and we had 84 cases with at least one serious adverse event or an event of special interest (the primary harm outcome). A simple extrapolation leads to an estimated rate of about 49% over 2 years (pooled over the whole blinded trial population, i.e. both treatment groups taken together). We have also performed life table analysis, which accounts for patients stopping prematurely; this analysis leads to an estimated rate of 40% (95% confidence interval: 30%-50%).

Given the above we can now assume with confidence that the base rate of patients with events in the placebo group will be substantially higher than originally predicted. This adds power to the trial: we need only between 400 and 450 patients to detect the originally targeted contrast of 27.5%/20% = relative risk of 1.38 (Table 1). At the expected pooled event rate of 40%, with 400 patients we have 80% power to detect a difference of 12% between placebo and prednisolone: i.e. placebo 34% and prednisolone 46%, a relative risk of 1.35. The results are better with 450 patients, and when the event rate is higher (Table 1). At the moment of submission of the amendment trial recruitment has been closed on December 31, 2018 at a total of 452 patients.

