6.4 Sample size calculation

In the main GLORIA trial, 225 patients per treatment group will be entered (total 450 patients).

In the chosen analysis strategy (see chapter 10), to detect differences in benefit (disease activity, radiographs) extensive RA trial experience (both for GC and other agents) has shown a sample size of 200 patients per group is amply sufficient. For example, in the CAPRA-2 study that compared modified release prednisone 5mg/d against placebo, the prednisone group had 231 patients, the placebo group 119 patients. The change in DAS28 after 3 months of treatment was -1.15 in the prednisone group, -0.63 in the placebo group; difference -0.52 (SE 0.13, p<0.001) ([Buttgereit F 2013](#)). However, the true incidence of adverse events (AEs) for GCs is currently unknown. Most relevant data to assess sample size adequacy for this study come from the reported CAMERA-2 trial ([Bakker MF 2012](#)). This trial randomized 236 early RA patients to tight-control high-dose methotrexate plus 10 mg prednisolone or placebo for two years. Interestingly, 22% of placebo patients compared to only 14% of prednisolone patients reported at least one serious AE or clinical event as defined in our protocol.

The original protocol used a base case expectation for a total of 20% of patients experiencing at least one event over two years in the placebo group and calculated a need for 400 patients in each treatment group, to have about 80% power to detect an increase of 7% (from 20% to 27% events; 90% power for an increase of 9%). However, based on our current experience the sample can be decreased to about 450 instead of 800.

Elaboration:

In Dec 2018 we had >400 patients in the trial with a mean follow up of 9 months, and we had 84 cases with at least one serious adverse event or an event of special interest (the primary harm outcome). A simple extrapolation leads to an estimated rate of about 49% over 2 years (pooled over the whole blinded trial

population, i.e. both treatment groups taken together). We have also performed life table analysis, which accounts for patients stopping prematurely; this analysis leads to an estimated rate of 40% (95% confidence interval: 30%-50%).

Given the above we can now assume with confidence that the base rate of patients with events in the placebo group will be substantially higher than originally predicted.

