This adds power to the trial: we need only between 400 and 450 patients to detect the originally targeted contrast of 27,5%/20% = relative risk of 1,38 (Table 1).

At the expected pooled event rate of 40%, with 400 patients we have 80% power to detect a difference of 12% between placebo and prednisolone: i.e. placebo 34% and prednisolone 46%, a relative risk of 1,35. The results are better with 450 patients, and when the event rate is higher (Table 1).

At the moment of submission of the amendment trial recruitment has been closed on Dec 31, 2018 at a total of 452 patients.

Table 1. Sample size scenarios (one-sided alpha 5%).

expected event rate over 2 years		with power 80%,			
(% unique patients with at least one event)		detectable rate in predn group		Relative Risk	
pooled	placebo	n=400	n=450	n=400	n=450
30%	26%	38%	37%	1,47	1,43
35%	30%	42%	41%	1,40	1,37
40%	34%	46%	45%	1,35	1,32
45%	39%	52%	52%	1,31	1,31
50%	43%	55%	55%	1,28	1,28

For the substudy to measure adherence, no formal sample size calculation has been done. In feasibility assessments in the centres, the proportion of elderly patients with a smartphone was about 20%. However, in our current experience this is true only in the Netherlands. All other countries have indicated none of their currently included patients has a smartphone. Assuming that patients with a smartphone are technically interested, we can expect about 80% of them to be willing to participate. This gives a total sample size of 50 patients (25 per group). No data is available on actual adherence or its variability between patients.

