**Table 1. Sample size scenarios (one-sided alpha 5%).**

expected event rate over 2 years		with power 80%,			
(% unique patients with at least one event)		detectable rate in predn group		Relative Risk	
pooled	placebo	n=400	n=450	n=400	n=450
30%	26%	38%	37%	1,47	1,43
35%	30%	42%	41%	1,40	1,37
40%	34%	46%	45%	1,35	1,32
45%	39%	52%	52%	1,31	1,31
50%	43%	55%	55%	1,28	1,28

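### Table 1 has a wrong detectable rate in its 45% row and a base-case relative risk at 450 patients of 1.32 that should be 1.34, and the original target is stated as both 27% and 27.5%; the sample size is unaffected.

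*SAP*

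**What the plan says.** SAP 6 sets the size: "In the main GLORIA trial, 225 patients per treatment group will be entered (total 450 patients"). It also records that "trial recruitment has been closed on December 31, 2018 at a total of 452 patients". Both documents print the same table, headed in the SAP "Sample size scenarios (one-sided alpha 5"%). For each assumed placebo event rate it gives, at 80% power, the detectable prednisolone rate in whole percents and the relative risk to two decimals, for 400 and 450 patients in total.

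- The base case, bold in the SAP, reads "40% 34% 46% 45% 1,35 1,32": pooled rate, placebo rate, detectable rate at 400 and at 450, relative risk at 400 and at 450.
- The next row reads "45% 39% 52% 52% 1,31 1,31".
- The text says of the table: "The results are better with 450 patients, and when the event rate is higher (Table 1").
- The original 800-patient design is described as having 400 per arm "to have about 80% power to detect an increase of 7% (from 20% to 27% events"). Shortly afterwards the same section calls the target the "originally targeted contrast of 27,5%/20% = relative risk of 1,38".

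**The concern.** A table that fixes power at 80% can be checked cell by cell. The 45% row fails on simple division: its printed rates do not give its printed relative risk. The base-case relative risk at the enrolled size is printed to two decimals, but it matches the ratio of the whole-percent rates and not the ratio at which power is 80%. The original target takes two values a few lines apart, and only one of them fits the stated power.

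Table 1 is the stated basis for the reduction from 800 to 450. The harm rule in SAP 4.12 counts a non-significant increase as success. Readers will therefore use this table to judge how large an increase the trial could have detected, and will quote 1.32 as that effect.

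**Working it through.** **Inputs.** One-sided alpha 5% and power 80% (Table 1); 1:1 allocation (protocol 9.2), so 200 or 225 per arm; placebo rates as printed. The documents name no sample size formula. I assumed the standard two-proportion test with pooled null variance, in line with the chi-square test in protocol 11.1, and no allowance for dropout.

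**Formula.** With n per arm and p̄ = (p1 + p2)/2:

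power = Φ{ [(p2 − p1) − 1.645·√(2p̄(1 − p̄)/n)] / √([p1(1 − p1) + p2(1 − p2)]/n) }

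**Step 1: the plan's own example.** 34% against 46%, n = 200: (0.12 − 1.645 × 0.0490)/0.0486 = 0.811, power 79.1%. This agrees with the stated 80% within rounding.

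**Step 2: every cell.** Solving for p2 at 80% power:

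| Placebo | Rate at 400: printed / computed | Rate at 450: printed / computed | RR at 400: printed / computed | RR at 450: printed / computed |
|---|---|---|---|---|
| 26% | 38 / 37.6 | 37 / 36.9 | 1.47 / 1.44 | 1.43 / 1.42 |
| 30% | 42 / 41.9 | 41 / 41.2 | 1.40 / 1.40 | 1.37 / 1.37 |
| 34% | 46 / 46.2 | 45 / 45.4 | 1.35 / 1.36 | 1.32 / 1.34 |
| 39% | 52 / 51.3 | 52 / 50.6 | 1.31 / 1.32 | 1.31 / 1.30 |
| 43% | 55 / 55.4 | 55 / 54.7 | 1.28 / 1.29 | 1.28 / 1.27 |

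Eight of the ten rate cells agree after rounding. The exceptions are the two 52% cells.

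**Step 3: the 45% row.** 52/39 = 1.33, not 1.31.
- n = 200: (0.13 − 1.645 × 0.0498)/0.0494 = 0.974, power 83.5%.
- n = 225: (0.13 − 1.645 × 0.0470)/0.0466 = 1.134, power 87.2%.
- 51/39 = 1.31, the printed relative risk, so the wrong entry is the rate.

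**Step 4: the base case at 450.**
- Exactly 45%: (0.11 − 1.645 × 0.0461)/0.0458 = 0.747, power 77.2% (77.4% with 452 patients).
- The 80% solution is 45.44%, which rounds to the printed 45%; 0.4544/0.34 = 1.34.
- The printed 1.32 equals 45/34. For any placebo rate that rounds to 34%, the relative risk at 80% power lies between 1.33 and 1.34, so rounding of the placebo rate does not explain 1.32.

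**Step 5: the original design, 400 per arm, 20% on placebo.**
- 27%: (0.07 − 1.645 × 0.0300)/0.0299 = 0.692, power 75.6%; relative risk 27/20 = 1.35.
- 27.5%: (0.075 − 1.645 × 0.0301)/0.0300 = 0.851, power 80.3%; 398 per arm needed; relative risk 27.5/20 = 1.375, printed as 1.38.
- 29% (the 9-point increase): power 90.7%, against a stated 90%.

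**Step 6: other methods.** For 34% against 45% at 225 per arm: unpooled variance 77.5%, arcsine 77.3%, log relative risk 76.4%, exact enumeration 77.0%, continuity-corrected 74.2%. For 39% against 52%, a continuity correction gives 80.9% at 400 patients, but 85.0% at 450. It also lowers the plan's own 34% against 46% example to 76.0%, so it cannot be the method behind the table.

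**The case against.** The strongest reply is that the table reports detectable rates in whole percents at a fixed 80% power, so putting a rounded rate back into the formula measures only the rounding. That largely stands, and it rules out several stronger readings:

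- A reader might infer from the 77% that the trial lacks 80% power at the enrolled size. It does not lack it: 450 patients give 80% power, at 45.4%, and the rate cell is right at its stated precision. Rounding also works the other way: 26% against 38% at 400 patients has 82.5%.
- A reader might call the 50% row wrong because its two columns are equal. Both 55.4% and 54.7% round to 55%, so its rates are correct as printed.
- A reader might take the equal columns to contradict "The results are better with 450 patients, and when the event rate is higher (Table 1"). Unrounded, 450 patients do better in every row, so the sentence is true. Whole-percent rounding hides the gain.
- A reader might infer that the original design had only 76% power. The section's own 27.5% gives 80.3% and reproduces 400 per arm, so the 7% is best read as a rounded 7.5 points. The defect is an inconsistent target, not a wrong power.

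Rounding could also rescue the 400-patient cell of the 45% row. A placebo rate just under 39.5% has a detectable rate just under 51.9%, which would print as 39%, 52% and 1.31. It cannot rescue the 450-patient cell: any placebo rate that rounds to 39% gives 50.1% to 51.1% and a relative risk of 1.29 to 1.30.

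Finally, the 52% error makes the trial look less sensitive than it is, and recruitment had already closed. Both are true, and they are why the point is minor.

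**Conclusion.** The point holds as a minor reporting error in both documents. The 52% cells should be 51.3% and 50.6%, with relative risks 1.32 and 1.30. The base-case relative risk at 450 patients should be 1.34 instead of 1.32. The original target should have one value.

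The sample size conclusion survives. At the 40% pooled rate the detectable relative risk is 1.36 with 400 patients and 1.34 with 450, both below 1.38. The 27% or 27.5% question matters a little here: against a literal 27% (relative risk 1.35), 450 patients would still suffice but 400 would just miss.

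These figures rest on a pooled two-proportion test, equal arms, placebo rates exactly as printed and no loss to follow-up. They do not assess the harm model in SAP 4.10.3.

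**What to change.** In protocol 6.4 and SAP 6:

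1. Print detectable rates to one decimal and compute every relative risk from unrounded rates. The base case at 450 patients becomes 34% against 45.4%, relative risk 1.34. This also updates the 30% row, whose printed 1.47 and 1.43 match neither its own rates (38/26 = 1.46, 37/26 = 1.42) nor the computed 1.44 and 1.42.
2. Replace the two 52% cells with 51.3% and 50.6%, relative risks 1.32 and 1.30.
3. State the original contrast once, as 20% against 27.5% (relative risk 1.38).
4. Name the test and variance formula under the table.

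The cost is a text and table edit. Design, analysis and decision rules do not change; the stated base-case detectable relative risk becomes slightly less favourable.
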